7.3 LOST TO FOLLOW-UP

A subject will be considered lost to follow-up if he/she fails to attend a scheduled study Visit (including treatments) and cannot be contacted by the study site staff, subject to the completion of the action detailed below:

- Within 2 days from the original missed study Visit, the site will attempt to contact the subject and reschedule the missed visit. The site will counsel the subject on the importance of maintaining the assigned visit schedule and ascertain if the subject wishes to and/or should continue in the study.
- Before a subject is deemed lost to follow-up, the Investigator or designee will make every effort to regain contact with the participant and his/her caregiver/s (where possible, 3 telephone calls and, if necessary, a certified letter to the subject's last known mailing address or local equivalent methods, a visit to subject's last known address where reasonable). These contact attempts should be documented in the subject's medical record or study file.
- Should the subject continue to be unreachable, he or she will be considered to have withdrawn from the study with a primary reason of lost to follow-up.

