7 STUDY INTERVENTION DISCONTINUATION AND PARTICIPANT DISCONTINUATION/WITHDRAWAL

7.1 DISCONTINUATION OF STUDY INTERVENTION

Any symptoms of treatment-emergent clinical deterioration in subject's condition requiring intervention of the medical team to alleviate these symptoms and qualifying for toxicity Grade 3 (or higher) on the CTCAE v.5.0 scale will result in a halt of administration of the study intervention for that treatment session; halting for a longer period of time will occur only if deemed necessary by the Investigator.

In general, discontinuation of administration of the study intervention, for any reason, does not mean discontinuation from the study, and the remaining study procedures should be completed as indicated by the study protocol, unless informed consent is withdrawn. If a clinically significant finding is identified (including, but not limited to changes from baseline) after enrollment, the Investigator or qualified designee will determine if any change in subject management is needed. Any new clinically relevant finding will be reported as an AE. For requirements on reporting of adverse events, serious adverse events and unanticipated problems please refer to §§ 8.3.5, 8.3.6, and 8.4.2, respectively.

The data to be collected at the time of discontinuation of administration of the study intervention will include the date and reason for discontinuation and any data on the adverse event(s), if applicable.

Women who become pregnant during the trial will continue to be assessed, including assessment of pregnancy outcomes, and investigational device administration will be discontinued. Further provisions on reporting of pregnancy, including period of reporting are in § 8.3.9.

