7.2 PARTICIPANT DISCONTINUATION/WITHDRAWAL FROM THE STUDY

Participants are free to withdraw from participation in the study or discontinue the study intervention at any time upon request. Those wishing to discontinue participation do not have to provide a reason; however, when appropriate, the site investigator should discuss the study, informed consent, and any on-going risks and benefits to continued participation with the participant.

In addition to discontinuation of administration of the study intervention (section 7.1), subject participation in the study may be terminated by the Investigator or the Sponsor if any one or more of the following conditions are met:

- occurrence of an unexpected serious adverse event;

	The efficacy of a frequency-tuned electromagnetic field treatment in facilitating the recovery of subacute ischemic stroke patients – a pivotal study		
	No. BQ5	Ver. 4	Page 58 of 150

- pregnancy;
- loss to follow-up (refer to § 7.3 for accompanying instructions); health conditions that require treatment that might affect the procedure and/or its outcome;
- significant protocol deviation (please refer to § 10.1.10) or noncompliance, either on the part of the subject or Investigator. These will include (but not limited to):
 - o enrollment in violation of the study eligibility criteria;
 - o performing the trial procedure not as prescribed in the BQ 2.0 IFU;
 - o other ethical or clinical considerations at the discretion of Investigator.
 - o enrollment in another interventional study overlapping with the period of participation in this study.

Data collected prior to withdrawal of consent will remain in the study database, but no further data will be collected on those who withdraw. Follow up on serious adverse events that are not resolved by the time that the subject leaves the study will be handled as defined in § 8.3.4. Follow up on pregnancy outcome will be handled as defined in § 8.3.9.

Withdrawn/discontinued randomized subjects will not be replaced.

If a subject withdraws from the clinical investigation, the reason(s) shall be recorded. Withdrawals will be recorded, analyzed, and reported to local IRBs/ECs as required.

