Data elements can be transcribed into the eCRF from paper or electronic source documents, other than hardcopy of the eCRF serving as source documents worksheet. For these data elements, the electronic or paper documents from which the data elements are transcribed are the source. These data must be retained by the Investigators and made available for inspection by the study Monitors and/or that of regulatory authorities, if requested (eg, an original or certified copy of a laboratory report, instrument printout, progress notes of the Investigator, the study participant's hospital chart(s), nurses' notes, patient/subject questionnaires).

⁵⁴ A certified copy is a copy (irrespective of the type of media used) of the original record that has been verified, (ie, by a dated signature or by generation through a validated process), to have the same information including data that describe the context, content, and structure, as the original (§ 3.7 of ISO 14155:2020)

Data to be collected in case of termination or withdrawal

Whenever participation of a subject is terminated, or subject withdraws from the study:

- a. all eCRFs, including follow-up, must be completed, regardless of treatment received, up to the point of withdrawal or termination.
- b. all data collected up to the point of withdrawal or termination will be maintained in the database and included in subsequent analyses.
- c. information obtainable from public records (eg, death) does not require consent. This information may be recorded on the appropriate eCRF.

Responsibilities

The eCRFs must be completed, signed and dated by the Investigator or his/her designee (as delegated on the Study Responsibilities Form/Delegation Log) within the time frame listed below ([Table 5](#)). The Investigator will be responsible for the timing, completeness, and accuracy of the subjects' CRF/eCRFs.

Table 5. Summary of CRF/eCRF forms completion time frame

eCRF	Schedule for CRF/eCRF completion
Screening visit	Within 1 day of completion.
Study Procedure	Within 5 days of completion.
Study Follow-up	Within 5 days of completion.
Safety events	Refer to §§ 8.3.5 and 8.3.6
Concomitant medications	Within 5 days of completion of relevant investigational product use.
Study Termination	Within 5 days of termination.

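### Section 7.3 can class a subject as withdrawn after one missed treatment session and failed contact, weeks before Day 90, with no renewed attempt at the primary mRS required

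*Protocol*

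**What the plan says.** Four parts of the protocol bear on this point.

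- **Section 7.3, trigger.** "A subject will be considered lost to follow-up if he/she fails to attend a scheduled study Visit (including treatments) and cannot be contacted". Each of the 45 sessions therefore counts as a visit that can start the process.
- **Section 7.3, steps before the label applies.** "Within 2 days from the original missed study Visit, the site will attempt to contact the subject and reschedule the missed visit". After that, "the Investigator or designee will make every effort to regain contact with the participant and his/her caregiver/s": three calls where possible, a certified letter if needed, and a home visit where reasonable.
- **Section 7.3, consequence.** "Should the subject continue to be unreachable, he or she will be considered to have withdrawn from the study", with lost to follow-up as the recorded reason. The section gives no minimum time before this applies and does not ask for another attempt when the Day 90 visit falls due.
- **Section 7.2.** "no further data will be collected on those who withdraw". The sentence opens by speaking of withdrawal of consent. The same section lists loss to follow-up among the grounds on which participation may be terminated.
- **Section 10.1.9.1.** When a subject withdraws or is terminated, case report forms are required only as far as that date. The section adds: "information obtainable from public records (eg, death) does not require consent. This information may be recorded on the appropriate eCRF".
- **Section 7.1.** Stopping the study intervention, whatever the reason, "does not mean discontinuation from the study, and the remaining study procedures should be completed as indicated by the study protocol"; the one exception is withdrawal of informed consent.

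**The concern.** A missed session is an event in the course of treatment. The primary endpoint is an mRS taken at day 90 (± 15). Section 7.3 ties the two together: if a session is missed and the contact attempts fail, the subject leaves the study and not merely the treatment schedule. Someone who cannot be reached in week 3 may be reachable in the day 75-105 window, and the protocol does not require anyone to try.

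What is at stake is a primary outcome that may have been obtainable. Section 8.1.1.6 allows the Day 90 visit by video or audio in special circumstances. The mRS form in Appendix 1 accepts relatives, therapists, physicians and the medical record as sources. Inclusion criterion 10 gives every subject an available caregiver.

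Readmission, a further stroke or death are plausible reasons for being unreachable, and each is related to the outcome. Section 9.4.2 takes missing Day 90 data to be missing at random because few dropouts are expected.

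**Working it through.** **1. The plan's own figure.** Section 9.2 uses a two-sample t-test with difference 0.5, SD 1, two-sided 5% and 80% power. This gives 63.77, so 64 per arm and 128 in total (power 80.1%). With 15% dropout, 128 / 0.85 = 150.6 against 150 stated, and 150 × 0.85 = 127.5. The sample size reproduces and this point leaves it unaffected.

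**2. How early the rule can apply.** The first session falls on day 4-21 after stroke (sections 6.1.2 and 8.1.1.3). The Day 90 window runs from 90 − 15 = day 75 to 90 + 15 = day 105. Sessions run five a week to 45 (section 6.1.1.5). I assume an uninterrupted schedule of five consecutive days each week, so session k falls on day start + 7 × floor((k − 1)/5) + ((k − 1) mod 5).

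| Session | Offset from start | Study day | Days before day 75 | Days before day 105 |
|---|---|---|---|---|
| 1 | 0 | 4-21 | 54-71 | 84-101 |
| 20 | 21 + 4 = 25 | 29-46 | 29-46 | 59-76 |
| 45 | 56 + 4 = 60 | 64-81 | −6 to 11 | 24-41 |

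A subject who misses session 1 and never starts treatment is outside the mITT set (section 9.3). For a subject in that set the earliest trigger is session 2, one day later: 53-70 days before the window opens and 83-100 days before it closes. The contact steps take further time, but the protocol sets no minimum for them.

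**3. The sections side by side.** Take a subject who misses a session, cannot be reached and has not withdrawn consent.

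- Under 7.3 the subject is considered withdrawn.
- Under 7.2, data collection stops for those who withdraw. If the clause covers only withdrawn consent, this subject is not included; if it covers everyone classed as withdrawn, the subject is.
- Under 10.1.9.1, forms end at withdrawal or termination. That rule does not mention consent, so it applies on either reading of 7.2.
- Under 7.1, stopping treatment leaves the remaining procedures in place, because consent was not withdrawn.

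A site cannot tell from these whether the Day 90 mRS is still due.

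**4. Consequence in the analysis.** The midterm mRS is tied to session 20, about day 29-46 (± 4 days). A subject closed out before it has no post-baseline mRS. The condition in section 9.4.2 that a subject have one or more post-baseline values is then not met, and LOCF has no post-baseline value to carry forward. The planned multiple imputation uses baseline features plus the last post-randomization value; for this subject the second input does not exist.

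**The case against.** The strongest reply is that being unreachable causes the loss, and the missed session does not. Section 6.1.2 has missed sessions rescheduled, and section 7.3 requires escalation to both subject and caregiver first. A subject who is reached is rescheduled and not closed out. This stands, and a reader who infers that a missed session by itself ends participation goes too far.

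A reader might also infer that the primary mRS will never be sought for these subjects. No section says so. The clause in 7.2 starts from withdrawal of consent, its list says participation may be terminated, and 7.1 points the other way. The text supports only that the mRS need not be sought and that the sections disagree.

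Deaths are partly covered. Section 8.3.5 requires all deaths to be reported to the sponsor, and death is already level 6 of the mRS in section 8.1. What remains is that the public-record search, the way to find a death the site has not heard of, is optional.

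The analysis does not rest on the mixed model alone. Section 9.4.2 adds multiple imputation for the mITT set and LOCF as a sensitivity analysis, and subjects lost after the midterm visit contribute that value. This limits the harm, chiefly for those later losses.

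A power loss of about three points is also tempting: 80.1% at 128 evaluable against 77.5% at 120. But 120 of 150 is 20% missing, above the 15% already allowed. The calculation ignores the repeated-measures model, and the protocol gives no rate for this route of loss.

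Finally, section 5.5 refers to a manual of procedures for retention detail, which is not at hand. It may call for later contact. It would not change the status that section 7.3 assigns.

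**Conclusion.** The point holds as a conflict between stated rules. Section 7.3 allows early classification as withdrawn with no minimum interval and no renewed attempt at Day 90. With 7.2 and 10.1.9.1, it permits a subject who has not withdrawn consent to be closed out without the primary mRS being sought. Section 7.1 says otherwise.

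The size that can be stated is timing: the first session lies 54-71 days before the Day 90 window opens and 84-101 days before it closes. These two ranges rest only on the start window and the visit window; the later rows of the table assume an uninterrupted schedule. Closure before the midterm visit leaves no post-baseline mRS. Neither the number of subjects affected nor the bias or loss of power can be derived from the protocol. The case for change rests on its low cost and on assessment routes the protocol already allows.

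**What to change.** Reconcile sections 7.1, 7.2, 7.3 and 10.1.9.1 so that:

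- (a) a missed session with failed contact is recorded as a treatment status and not as withdrawal from the study;
- (b) lost to follow-up for the primary endpoint is assigned only after a documented attempt to reach subject and caregiver inside the Day 90 window, with remote mRS allowed, has failed;
- (c) the stop on further data applies only to withdrawal of consent;
- (d) the public-record vital-status check is required for subjects unreachable at Day 90, with any death found entered at the existing mRS level 6.

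The cost is amendment wording plus a few more calls and record checks. No visit is added.

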8 STUDY ASSESSMENTS AND PROCEDURES

8.1 EFFICACY ASSESSMENTS

The order of and timeline of the screening procedures and evaluations (Visit 1) are presented in the study schema (please refer to § 1.2) and the schedule of activities (please refer to § 1.3).

The questionnaires and functional tests detailed below are appended to this protocol (please refer to § 12.1).

mRS (first screening procedure after consent is obtained)

The mRS is a 7-level scale with possible scores ranging from 0 (no symptoms at all) through 5 (severe disability) and 6 (death) and is used for measuring the degree of disability or dependence in the daily activities of people who have suffered a stroke or other causes of neurological disability (76). The mRS is the most frequently used outcome measure in stroke trials (77). To increase outcome comparability and minimize bias, the modified Rankin Scale assessments of global disability will be obtained at all sites using the formal, algorithmic Rankin Focused Assessment-Ambulatory (RFA-A) method by RFA-A-certified raters (78-80). The formal RFA-A elicitation technique is an NIH trial-developed method for assigning mRS scores validated to improve inter-rater reliability in assigning mRS scores. In addition, the RFA-A method to assign mRS scores has been employed for primary and second endpoint ascertainment in numerous FDA-regulated drug and device trials (47, 81-83).

Fugl-Meyer Assessment-Upper extremity (FMA-UE; second screening procedure)

The Fugl-Meyer Assessment is a stroke-specific, performance-based impairment index. It is designed to assess motor functioning, balance, sensation and joint functioning in patients with post-stroke hemiparesis (84, 85). It is frequently applied clinically and in research to determine disease severity, describe motor recovery, and to plan and assess rehabilitation treatment (86). This test is one of the most used instruments in rehabilitation and its validity and reliability has established validity, reliability, and sensitivity to treatment-related change (84, 87, 88).

In this study, the index will be used to assess the motor impairment of the upper extremity after stroke. Each movement will be graded on a 3-point scale, and the total score will range 0–66 points, with a higher score representing more active movements.

	The efficacy of a frequency-tuned electromagnetic field treatment in facilitating the recovery of subacute ischemic stroke patients – a pivotal study		
	No. BQ5	Ver. 4	Page 60 of 150

Box and Block Test (BBT)

The Box and Block Test is a quick and simple test which measures unilateral upper extremity function (89). In the BBT, one hundred and fifty 2.5-cm³ wooden blocks in many different orientations are placed on the side of the partition with the testing hand. A subject's score is equal to the number of these blocks transported over a 15.2-cm-tall partition in one minute. The subject can select blocks in any order to transport over the partition as quickly as possible, with the only requirement being that the subject's fingertips cross the vertical plane of the partition (90).

Stroke Impact Scale (SIS) Hand-Domain and SIS-16

The Stroke Impact Scale is a patient reported outcome instrument designed to assess physical function in patients with stroke. This outcome measure developed in the United States by Duncan et al (91, 92) and has undergone considerable validation and development. The SIS was designed for in-person use, but can be administered via phone or mail, too. The SIS Hand-Domain (SIS version 3.0) assesses hand function, including activities dependent upon grip, pinch strength, and finger dexterity (93).

The SIS-16 assesses physical function, including activities dependent upon upper extremity, lower extremity, trunk, and gait motion (94).

EQ-5D-5L

The EuroQol-5 Dimension (EQ-5D), developed in 1990, is a widely used generic tool to measure generic health-related quality of life (HRQoL) using three levels of severity in five dimensions (95). In 2009, the EuroQol Group developed a new EQ-5D version to overcome limitations related to its consistently reported high ceiling effect. To enhance the sensitivity for assessing HRQoL in further patient populations, the number of responses for each section of the EQ-5D was increased from 3 to 5 levels (EQ-5D-5L; (95)). EQ-5D scores can be converted to patient-specific health utilities that are used in the calculation of quality-adjusted life years and evaluating the cost-effectiveness of medical therapies.

10-meter walk test (10MWT)

The 10-meter walk test is a simple assessment to measure locomotor capacity in clinical and research settings. The individual walks alone or with assistance of no more than one person and their gait velocity is quantified. Assistive devices which are normally used for balance and/or stability (eg, cane or walker) are allowed. Individuals are requested to walk the said distance in their usual or normal pace. The mean velocity of gait has been termed the sixth vital sign (96) because of its very high clinical, research, and real-world relevance.

	The efficacy of a frequency-tuned electromagnetic field treatment in facilitating the recovery of subacute ischemic stroke patients – a pivotal study		
	No. BQ5	Ver. 4	Page 61 of 150

Academic Medical Center Linear Disability Score (ALDS)

The Academic Medical Center Linear Disability Score is a generic item bank that measures the disability status of patients with a broad range of diseases, as expressed by the ability to perform activities in daily living (97). Using the ALDS, disability level can be quantified in a granular fashion on a continuous scale, using ~15 items tailored to the particular general functional level of each patient.

MoCA

The Montreal Cognitive Assessment is a widely used screening assessment for detecting cognitive impairment developed in Montreal Canada. It is a one-page, 30-point test administered in approximately 10 minutes (98).

PHQ-8

The Patient Health Questionnaire (PHQ) is a self-administered version of the PRIME-MD diagnostic instrument for common mental disorders (99). The PHQ-8 is composed of 8 items that assess for depression based on DSM-IV criteria, with each item rated between “0” (not at all) to “3” (nearly every day) (99). The PHQ is an instrument for making criteria-based diagnoses of depressive and other mental disorders commonly encountered in primary care. The PHQ-8 does not include the ninth item of the PHQ-9, as that item has been found not to be reliable and the PHQ-8 performs comparably to the PHQ-9. The PHQ-8 is half the length of many other depression measures, has comparable sensitivity and specificity (99). The PHQ-8 is more efficient than “2-step” depression measures for which, when scores are high, additional questions must be asked to establish DSM-IV depressive diagnoses. Specifically, the diagnostic validity of the PHQ in post-stroke patients has been established in several studies (102-110).

8.1.1 STUDY VISITS

8.1.1.1 PRE-SCREENING PHASE

Prospective subjects, who are 3 to 21 days post-stroke, can be consented to participate in the study at a participating initial acute care hospital (ACH) prior to anticipated discharge to a participating IRF, SNF, outpatient, or home setting. Alternatively, prospective subjects, who are 3 to 21 days post-stroke, can be consented at a participating IRF, SNF, outpatient, or home setting.

Only brief eligibility review to determine initial eligibility and interest in the study will be performed prior to elicitation of consent.

8.1.1.2 SCREENING & ENROLLMENT, BASELINE VISIT

Efforts should be made to complete enrolment, randomization and initiate treatments as early as possible within the window of recruitment, and target to complete a first treatment within 4 weekdays from admission to the participating site.

For consented subjects, the following additional data will be recorded at this visit:

- Demographics – age, sex, race/ethnicity
- Medical history - presence of concomitant medical conditions (eg, hypertension, diabetes, hyperlipidemia, atrial fibrillation, prior ischemic stroke, prior hemorrhagic stroke, current or past smoking)
- Vital signs – temperature, pulse, blood pressure.
- Concomitant medications – any concomitant medications by or administered to the subject at the time of screening (for details, refer to § 6.5).
- In women of childbearing potential a urine or blood test will be performed unless there is a documentation of a negative pregnancy test in an official medical documentation.
- mRS
- FMA-UE,
- BBT,
- 10MWT
- SIS Hand Domain,
- SIS-16,
- SAFE
- NIHSS
- Any adverse events

Consented subjects, who are 4 to 21 days post-stroke, and have passed screening for eligibility will advance to the treatment phase of the study, commencing with randomization.

Randomization should be performed within 24 hours from the mRS and FMA-UE assessments. If more than 24 hours have elapsed, these assessments should be repeated and only those subjects whose reassessed scores for both assessments conform with the eligibility criteria will be randomized. The later scores will serve as the baseline scores and for stratification.

Eligible subjects will be randomly assigned, at a 1:1 allocation ratio, to either the active or sham study intervention groups.

The following additional data will be obtained after randomization and not later than Midterm follow-up visit:

	The efficacy of a frequency-tuned electromagnetic field treatment in facilitating the recovery of subacute ischemic stroke patients – a pivotal study		
	No. BQ5	Ver. 4	Page 63 of 150

- Imaging Data – there will be no imaging tests performed in the study. However, for subjects randomized to the study, all computed tomography (CT), CT angiography (CTA), CT perfusion (CTP), and brain magnetic resonance imaging (MRI) perfusion/diffusion-weighted imaging (DWI/PWI) / fluid attenuated inversion recovery brain magnetic resonance angiography (FLAIR), and brain magnetic resonance angiography (MRA) studies available from the first 7 days in the ACH will be transferred to the sponsor by either using CD's or via an online cloud based service. If multiple images are available from different recording sessions at the acute stay, it is required to collect the first image and the last image²⁷. Please refer to the study MOP for instructions.
- The following values from the complete blood count performed at the time the subject was admitted and diagnosed with stroke will be transcribed into the CRF:
 - red blood cell distribution width (an independent predictor of 3-month functional outcome; (111))
 - absolute white cell count (an independent predictor of stroke severity and degree of disability; (112))

